6.3 Adverse Event Grading and Coding

AEs will be coded, grouped and tabulated by MedDRA preferred terms by body system organ class. The MedDRA version current at study initiation will be used for the entire study.

Adverse events will be graded according to US National Cancer Institute Common Terminology Criteria for Adverse Events [NCI CTCAE] v5.0. The following are the general criteria for severity grading:

Grade	Description
1	Mild
2	Moderate
3	Severe
4	Life-threatening or disabling
5	Fatal

The NCI CTCAE v5.0 can be downloaded in pdf format at:

https://ctep.cancer.gov/protocolDevelopment/electronic applications/docs/CTCAE v5
Quick Reference 8.5x11.pdf

6.4 Handling of Serious Adverse Events

Adverse events classified as serious must be recorded on the AE page of the CRF and require expeditious handling and reporting to the sponsor to comply with regulatory requirements. These SAEs will include deaths, regardless of their causal relationship to investigational product. All SAEs must be reported using the Serious Adverse Event Report form. To the extent possible, the descriptive terminologies and other SAE attributes entered on the SAE report form should approximate similar information in the CRF. The completed SAE report form with supporting documentation must be provided to the sponsor within 24 hours of the study site personnel's initial notification/awareness of the event. All telephone communication regarding SAE must be followed by a written report. Duly authorized study site personnel may sign completed SAE report forms; however, it is recommended that the investigator sign each final SAE report.

Collection of complete information concerning SAEs is extremely important. Thus, follow-up information that becomes available as the SAE evolves, as well as supporting documentation (e.g. hospital discharge summaries, additional lab and test results, autopsy reports, etc.), should be collected subsequently, if not available at the time of the initial report, and immediately sent to sponsor using the same procedure as the initial SAE report. Information on the SAE must be in sufficient detail to allow for a complete medical assessment of the case and independent determination of causality.

For ease of analysis, worldwide standardization, and regulatory reporting, the sponsor will code each reported adverse event or symptom to its corresponding preferred term and body system/organ class in the MedDRA dictionary version adopted for the study. The principal investigator will be responsible for assessing severity based on the intensity of the event as it presented using the criteria listed in section 6.3, above.

All SAE reports must be sent to the study medical monitor and the sponsor's regulatory/clinical affairs contact:

Medical Monitor: [name]

Mobile [contact] or

[contact]

e-mail: [contact]

Pharmacovigilance officer: [name]

Email: [contact]
Phone: [name]

Additional pharmacovigilance contacts

will be provided for ex-US sites

As required, all investigators will be notified of all AE reports that are determined to be serious, unexpected, and related (by the reporting investigator or sponsor) to the investigational product. The notification will be in the form of a Safety Update (Dear Doctor Letter).

The notification is considered an addendum to the current Investigator's Brochure; therefore, upon receiving such notices, the investigator must review and immediately submit a copy to the IRB according to local regulations. The notification must be retained within the Investigator's Brochure. The investigator and IRB will determine if the informed consent requires revision.

6.5 Laboratory Test Abnormalities

All new abnormal laboratory findings and those abnormal at baseline which change significantly (i.e., by at least one toxicity grade as defined in the National Cancer Institute Common Terminology Criteria for Adverse Events [NCI CTCAE] v5.0) are considered AEs. Laboratory AEs for which there is no clinical intervention will be recorded only on the laboratory data pages of the eCRF. Laboratory AEs not listed in the NCI CTCAE v5.0 will be considered as grade 1 (mild) if there is no clinical effect or intervention. Laboratory values outside the normal range for certain parameters will not be considered AEs if they are generally not considered as indicating an abnormality; this includes such parameters as liver enzymes which are below the normal range. If there is a clinical sequela or intervention, the laboratory abnormality is to be graded according to the criteria used for clinical AEs, described above.

The NCI CTCAE v5.0 can be downloaded in pdf format at:

https://ctep.cancer.gov/protocolDevelopment/electronic_applications/docs/CTCAE_v5_Quick_Reference_8.5x11.pdf

6.6 Other Safety Considerations

Patients will be followed for a total of 8 weeks from the start of study medication. After the enrolment visit until the end of study visit, direct contacts between study personnel and patients may be entirely by home and televisits. Alternatively, at the mutual convenience of patients and study staff, one or more of the interim visits may be held at the investigative site. In some instances, in particular for significant exacerbations of disease or adverse events regardless of relationship to study medication, the patient will come to the medical facility for an in-person assessment.

All AEs must be recorded and followed until resolution or for at least 28 days after discontinuation of study medication, whichever comes first.

Any clinically significant changes noted during interim or final physical examinations, electrocardiograms, x-rays, and any other potential safety assessments, whether or not these procedures are required by the protocol, should also be recorded on the AE page of the CRF.

7. Data Analysis and Statistical Considerations

This section of the protocol describes the statistical analysis as it is foreseen at the time of planning the study. A fully detailed Statistical Analysis Plan (SAP) will be produced and finalized after finalizing the protocol and before breaking the blind of the study for interim analysis.

The SAP will be reviewed after analysis of data from part A. Modifications may be made to the analyses planned for part B based on that review. The revisions will be finalized before reaching the interim analysis point for part B.

7.1 Sample Size Considerations

Part A

In the first part of this study, two different dose levels of upamostat will be tested; randomization will be 1:1:1 to the two upamostat dose levels and placebo.

The objective of this part is to evaluate the tolerability of two dosing levels of upamostat in order to select the dose level that will be evaluated in the confirmatory Part B of the study.

The sample size for part A, consisting of 20 subjects per each arm (placebo, upamostat 200 mg qd, upamostat 400 mg qd) was not chosen for statistical power consideration, as there are no formal statistical inferences planned. The size of this part is judged adequate for the tolerability assessment.

Part B

After accrual to the first part of the study is completed and a determination as to which active arm to continue into the next part of the study is made, accrual will continue at a 3:2 ratio, active:placebo. A minimum total of 250 patients will be accrued to part B, 150 to the active arm using the regimen selected in part A of the study and 100 to placebo.

The sample size currently shown for part B was determined based on the primary endpoint, time to sustained recovery from COVID-19 illness, as defined in the primary objective. It was calculated that in order to detect a hazard ratio for sustained recovery=1.5 comparing the active group to placebo group with 3:2 allocation ratio, a total of 201 recovery events are required, to provide 80% power using a log-rank test at a two-sided significance level of 0.05. Assuming 80% sustained recovery rate in the control arm by end of follow-up (assumed equal follow-up of 57 days for all enrolled patients), it was calculated that in order to achieve the required number of events, the minimum number of patients enrolled will be 250 in total. As this study is defined as an operationally seamless phase 2/3 study, subjects from the part A of the study will not be combined with those in part B for the efficacy analysis. Therefore the target enrollment for part B is the total number of required subjects, namely 250 subjects in total, 150 and 100 for the active and placebo groups, respectively.

The target number of events for this event-based part B portion is 201, taking into account a non-binding futility analysis that will be performed when 50% of the information (primary events) have been realized.

Sample size re-assessment

In light of the limited information currently regarding time to sustained recovery and incidence of hospitalization or death expected in the control arm, and /or to address the

possibility that the magnitude of upamostat effect may be smaller than the relatively large target effect size but is still trending in the right direction and is big enough to be of clinical relevance, sample size re-assessment will be performed.

The sample size of 250 subjects was predicted to be sufficient to provide the required total 201 'recovery' events (assuming 80% sustained recovery rate by study day 57, in the control arm). The study design plan for part B is to continue recruitment until there are at least 201 subjects with a "recovered" status, if more than 250 subjects are needed for this.

If part A results suggest that the initial assumptions above should be altered, an updated target number of events and/or number of subjects will be predefined for part B.

In part B, sample size re-estimation, the results of which will be unblinded only to the DSMB, will take place when about 50% of target primary endpoint recovery or hospitalization or death events have been realized, to allow increasing the target event size by 50% (that is to a maximum of 301), thus requiring an associated increase of the sample by 50% (that is to a maximum of 375 subjects), only in the case that interim results falls within a "promising zone", as strictly defined in Chen et al, 2004, and Mehta and Pocock, 2011. Using this approach, a valid (using the conventional statistic for the final analysis, and the type-1 error not inflated) increase in sample size following an unblinded comparative look is allowed when the observed interim treatment effect, although smaller than hoped for, is still trending in the right direction and is of clinical relevance.

To safeguard study integrity, the pre-specified rules will be documented separately, in the DSMB charter.

If at the end of part A, the study is repowered to achieve statistical significance for the hospitalization or death endpoint, the incidence of this endpoint in the treatment groups in part A as well as literature data will be considered in determining the sample size for part B. This will take into account not only overall results of part A but also results in patients who are defined as high risk. It is understood that these calculations are based on a very small database, which may prove to be very imprecise.

If part B of the study is repowered, the timing of the interim analysis may be adjusted. At the interim analysis, the incidence of hospitalization or death in the high risk group, defined as patients with one or more of the concerning conditions listed in Section 4.1, may be modified. A higher risk group may be defined in order to establish an adequate incidence level of hospitalization or death in a well-defined subgroup to ensure the study is adequately powered for the analysis of this endpoint in a meaningful patient population. This may result in a revised sample size and limiting or redefining recruitment in the different subgroups. Sample size reassessment for the primary endpoint will only be conducted if the revised sample size is lower than the maximum sample size proposed for the primary endpoint as above.

7.2 Analysis Datasets

The primary and most secondary efficacy analyses will be performed on the modified intent to treat (mITT) population, defined as all randomized patients who receive any treatment. A per protocol (PP) analysis will be performed on patients with no major protocol violations and who receive at least one week of study medication or the reason

for stopping medication is worsening COVID-19 or development of AEs. In these analyses patients will be analyzed according to their randomized treatment. Analysis for the first secondary endpoint, hospitalization or death, will be performed primarily on a subset of the mITT population, the high risk or very high risk subset to be defined at the end of part A and redefined at the interim analysis of part B.

Formal efficacy analyses will be performed using part B enrolled subjects, the efficacy data from part A subjects will be descriptively summarized separately.

Safety analyses will be performed on all patients who receive any study medication in parts A and B combined, according to the treatment actually received.

7.3 Study Population and Demographics

Demographic and pretreatment patient characteristics, including disease parameters and comorbidities, will be summarized with appropriate descriptive statistics, by study part, overall and by treatment group. The descriptive statistics will include sample size, mean, standard deviation, median, minimum, and maximum for continuous variables and number and percentages for discrete variables.

7.4 Efficacy Analyses

7.4.1 Analysis of the primary efficacy endpoints

The primary endpoint of the study is time to sustained recovery from COVID-19 illness, as defined in section 2 of the protocol. The first secondary endpoint, incidence of hospitalization or death, will primarily be assessed in the high risk or very high risk population.

Time to sustained recovery is the number of days from first dose of study medication until the day on which patient is recovered and remains recovered for at least 14 days or until end of study, whichever comes first. The definition of "sustained" may be modified, as noted above, at the end of part A. First date of recovery will be defined as the **latest** time among the events below:

- 1) Start date of the period during which the patient is afebrile for at least 48 hours without use of antipyretics;
- 2) First date when all symptoms have resolved or returned to pre-illness levels (e.g., if patient had baseline respiratory compromise), except for
 - a. fatigue, anosmia, ageusia or dysgeusia, which may be persistent at levels similar to the acute illness, or
 - b. dyspnea, cough or chest pain, which, if persistent, must be at least one grade lower than baseline and no worse than grade 1 (mild).

Time will include the first day of study medication and the day on which patient is declared to have recovered.

Patients who have reached day 57 from the start of treatment but have not recovered will be censored at day 57. In addition, several situations override the above definition of recovery:

 Patients lost to follow-up during treatment or follow-up (before recovering) will be censored at day 57.

- Patients who recover per the definition above but are subsequently hospitalized for any reason and are in hospital at day 57 will be censored at day 57.
- Patients who die before recovery will be censored at day 57, the end of follow-up, reflecting the most unfavorable possible outcome for this endpoint.

Calculation of time to sustained recovery requires completion of the symptom diary. If a patient is hospitalized, he or she will be considered as not recovered on those days, regardless of the reason for hospitalization.

Supportive analysis will be performed to include recovery from viral shedding in the definition of recovered event. In this analysis time to recovery will be the latest between the two events above and time of first negative nose viral swab.

The comparison of the time to sustained recovery between active and placebo groups will be performed using stratified log-rank test, at 5% significance level. The stratification factors used for randomization will be used. Kaplan-Meier plots of time to sustained recovery will be provided along with median estimates and hazard ratio (HR) will be estimated along with 95% confidence interval using stratified Cox regression model. Estimates of cumulative incidence of sustained recovery at certain time points (for example days 15, 29, 43 or 57) for each group, along with 95% confidence interval will be tabulated.

More details on statistical analyses of the primary endpoint and sensitivity analyses will be provided in the SAP. These will address the following aspects:

- Using the PP population and ITT population
- To account for the possibility of errors in values of stratification factors used for randomization, the primary analysis will supportively be repeated using the correct values.
- Comparison between the treatment and control groups when controlling for
 possible imbalance in important baseline factors will be analysed by evaluating
 the HR obtained from estimating a multiple proportional hazards Cox regression
 model.

Subgroups to be analyzed, such as various risk categories, will be enumerated in the SAP. Handling of missing data will be described in the SAP.

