Under this amendment, the study procedures have been modified taking into account experience with the first patients entered into the study, as well as reasons patients have declined to participate. To date, symptoms have resolved in one to under three weeks. Patients have been resistant to the heavy monitoring and questioning in the original protocol, resulting in reluctance to participate in the study, withdrawal of several patients and poor compliance with study procedures. In order to enhance acceptability, accrual and compliance with the protocol, the duration of intensive vital sign monitoring is being reduced. In addition, the definition of sustained recovery is modified to take into account the patient compliance issue and experience to date with those patients who have recovered. If a substantial proportion of patients withdraws prior to the end of study *because* they feel better and the burden of study procedures is excessive, their efficacy results will be censored and those patients will be declared nonresponders. Temperature will be followed through 28 days after resolution of fever, if the patient is febrile, but with lower frequency from day 15 onward after resolution of fever.

Hospitalization or death has been moved to become the first secondary endpoint. FDA views this endpoint as that for which potential emergency use authorization is justified.

2. Objectives

Primary

Part A of the study: determination of the safety and tolerability of two dose levels and selection of an upamostat dose for part B. Part B of the study:

Primary objective: in the entire patient population, comparison between upamostat and placebo in time to sustained recovery from symptomatic illness in all patients. A patient will be considered to have recovered once he or she meets the following criteria:

- 1) is afebrile (<38.0° C core temperature) for at least 48 hours without use of antipyretics;
- 2) all symptoms have resolved or returned to pre-illness levels (e.g., if patient had respiratory compromise prior to the onset of COVID-19), except for:
 - i. fatigue, anosmia, ageusia or dysgeusia, which may be persistent at a level similar to that during the acute illness, i.e., the same level per symptom questionnaire;
 - ii. chest pain, cough or dyspnea, which if persistent must be at least one grade lower than at the start of treatment and no worse than grade 1 (mild).

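### Part B has no settled rule for patients who recover but leave before confirmation, and no listed analysis tests holding patients lost before recovery at risk to day 57

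*Protocol*

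**What the plan says.** **Lost before recovery.** Protocol 7.4.1 states: "Patients lost to follow-up during treatment or follow-up (before recovering) will be censored at day 57". SAP section 12 repeats the rule. Protocol 7.4.1 gives a worst-case reason for treating deaths this way and none for losses.

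**Recovered, but gone before confirmation.** Four places bear on these patients:
- Protocol 1.3 has a trigger, "If a substantial proportion of patients withdraws prior to the end of study" because they feel better and find the procedures too burdensome, and a consequence: "their efficacy results will be censored and those patients will be declared nonresponders". No threshold is given.
- Protocol 7.4.1 counts a patient who "remains recovered for at least 14 days or until end of study, whichever comes first". The secondary objectives equate end of study with day 57, and 7.4.1 calls day 57 the end of follow-up. Footnote b to Table 1, however, moves the end-of-study procedures to the time of discontinuation for early leavers.
- SAP section 12 treats recovery as not sustained once the diary gap exceeds 4 consecutive days, or 3 consecutive reporting days after day 28. No share of withdrawals is involved. This SAP covers part A; the part B SAP is still to be written (SAP section 1).
- The optional alternative definitions in SAP appendix 20.1.1 let the confirmation window close at the last observation.

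**Sensitivity analyses.** Protocol 7.4.1 lists the PP and ITT populations, corrected strata and a covariate-adjusted Cox model. SAP appendix 20.1.1 lists only other recovery definitions. None changes the censoring of losses.

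**Sample size.** Protocol 7.1 and SAP 5.4 size part B with "assumed equal follow-up of 57 days for all enrolled patients". Protocol 7.1 adds: "The study design plan for part B is to continue recruitment until there are at least 201 subjects" with recovered status, if more than 250 patients are needed.

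**The concern.** A patient who recovers on day 10 and stops reporting on day 18 could be an event on day 10 or a failure held to day 57. Which applies depends on which sentence is followed and, under Protocol 1.3, on how many other patients withdraw. That makes event status on the primary endpoint depend on the accumulating data. The situation is not remote: Protocol 1.3 reports that several patients have already withdrawn, and it anticipates leaving because patients feel better.

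Both kinds of leaver matter for the same reason. A patient held to day 57 without a possible event stays in every later risk set. With equal leaving this pulls the hazard ratio (HR) for recovery towards 1. Recruiting on to 201 recoveries replaces missing events but does not undo that dilution.

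The timing matters too. The part B interim uses unblinded primary-endpoint results for futility and sample-size increase (Protocol 4.8 and 7.1), so the rule must be fixed before then.

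**Working it through.** **1. The plan's own figure.** Inputs from Protocol 7.1: HR 1.5, allocation 3:2, two-sided 0.05, 80% power.

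Schoenfeld events = (1.960 + 0.842)² / [0.6 × 0.4 × (ln 1.5)²] = 7.849 / 0.03946 = 198.9, against 201 stated. Power at 201 events = Φ(√(201 × 0.24) × ln 1.5 − 1.960) = Φ(0.856) = 80.4%. Patients = 201 / 0.80 = 251.25, against 250 stated. The figures reproduce, with no allowance for leavers.

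**2. Base case at the stated minimum of 250.** Placebo recovery by day 57 is 80%. With proportional hazards, active recovery is 1 − 0.2^1.5 = 91.1%. Expected events = 150 × 0.911 + 100 × 0.80 = 216.6. Simulated power with no leavers is about 82%.

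**3. Assumptions for leaving.** The documents give no drop-out rate. The simulations use 150 v 100 patients, exponential recovery times and an unstratified log-rank test. Separate sets of runs agree to about one percentage point.

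**4. Lost before recovery.** The leaving rate is the probability of leaving over 57 days, equal in both arms and unrelated to recovery. Only patients who leave before recovering are affected: about 4–5% of patients at 10% leaving and 8–10% at 20%.

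| Leaving | Power, day-57 rule | Power, last-contact censoring |
|---|---|---|
| 5% | about 80% | about 81% |
| 10% | about 78% (HR 1.48) | about 81% |
| 20% | about 72% (HR 1.45) | about 79% |

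**5. Recovered, but gone before confirmation.** Here 10% or 20% of recovered patients leave, evenly over the 28 days after recovery. Unconfirmed recoveries fail and are held to day 57.

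| Recovered who leave | 14-day confirmation | 28-day confirmation |
|---|---|---|
| 10% | about 71% | about 62% |
| 20% | about 61% | about 44% |

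Counting these patients on their first recovery day keeps about 82%. Three of the four settings need more than 250 patients to reach 201 events. Recruiting on recovers little:
- 14-day, 20%: 257 patients, 62.7%;
- 28-day, 10%: 255 patients, 62.0%;
- 28-day, 20%: 283 patients, 48.0%, because the HR has fallen to 1.32.

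**6. Shape of recovery.** Protocol 1.3 reports: "To date, symptoms have resolved in one to under three weeks". Spreading recovery evenly over days 7–21 gives 80/78/73% in place of the day-57 column in step 4, and 71/61% (14-day) and 61/44% (28-day) in step 5. The exponential assumption does not drive the result.

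**7. Type I error.** With no drug effect and equal leaving, rejection is 5.1–5.2% under the day-57 rule. A hypothetical 10% active/20% placebo split, unrelated to recovery, gives about 7.4%, against 5.2% with last-contact censoring. If the same split leaves 1–5 days before recovery, the figures are about 24% and 11%, so neither rule protects the error rate there.

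**The case against.** **Day-57 censoring is a legitimate choice.** It treats loss as non-recovery, as the plan does for death. Last-contact censoring assumes leaving is unrelated to recovery, which Protocol 1.3 puts in doubt. This stands: the day-57 rule need not be replaced, only tested.

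**Much is deferred.** Protocol 7.4.1 sends missing data and further sensitivity analyses to the SAP, and the part B SAP does not yet exist. This stands as to timing. It does not cover the conditional rule in Protocol 1.3, which is a stated rule rather than a missing detail.

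**There are safeguards.** Part A results may reset the targets, the sample size may rise to 301 events and 375 patients, and procedures were lightened to reduce withdrawal. These give partial cover: the increase applies only in the promising zone, and none of them settles event status. The power figures above do not reflect them.

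**Stronger readings that the documents do not support:**
- A reader might infer that recovered leavers fail only if the trigger in Protocol 1.3 is met. In part A, the SAP diary-gap rule fails them whatever share withdraws, and the SAP takes precedence.
- A reader might infer that end of study is undefined. It has two readings, both in the text.
- A reader might infer that the 201-event target leaves power below the step 4 figures at low leaving rates. At 10% leaving, 201 events would come from about 240 patients, below the stated minimum of 250; at 250 about 209 events are expected.
- A reader might infer that the rule inflates type I error. That needs unequal leaving, which nothing in the documents suggests for this double-blind trial.

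**Conclusion.** The point holds and should be fixed. The main part is the unreconciled handling, in part B, of recovered patients who leave before confirmation, with a trigger that depends on the data and has no threshold. If such patients fail, the assumed 10–20% leaving costs about 11–21 percentage points of power with 14-day confirmation (82% to 71/61%) and 20–38 with 28-day (82% to 62/44%).

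The smaller part is the untested day-57 rule for losses before recovery. Compared with last-contact censoring, it costs about 3 points at 10% leaving and 7 at 20%. At 5% the cost is negligible.

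All these sizes rest on assumed leaving rates, equal in both arms, with 250 patients, 80% placebo recovery and HR 1.5. The stated 201 events and 250 patients are correct on their own terms. The result is a risk to power and to the clarity of the endpoint; it is not evidence of a biased test.

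**What to change.** 1. Reconcile Protocol 1.3, Protocol 7.4.1 and the diary-gap rule of SAP section 12, in the protocol and the part B SAP. Delete the share-based trigger, say whether end of study means day 57 or the patient's exit, and apply one unconditional rule. For example, the primary analysis could keep the conservative rule (unconfirmed recovery is censored at day 57), with a sensitivity analysis counting these patients as recovered on their first recovery day. The opening of Protocol section 7 already sets the deadline: "The revisions will be finalized before reaching the interim analysis point for part B".
2. Keep day-57 censoring as primary for losses before recovery. Pre-specify one sensitivity analysis that censors losses and withdrawals at the last completed diary day, with deaths kept at day 57.
3. In Protocol 7.1, state that 80% power assumes no loss before recovery and no unconfirmed leavers, and give power over an assumed range such as 5–20%.

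The cost is wording in Protocol 1.3, 7.1 and 7.4.1 and in the part B SAP, plus one or two analysis runs and no new data. The downsides are a less favourable stated power and two sensitivity analyses with assumptions of their own: last-diary censoring is biased if leaving is related to recovery, and counting leavers as recovered assumes no relapse after they go.
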